## 7.2. Secondary Efficacy Analyses

### 7.2.1. Secondary Efficacy Analysis

The secondary efficacy endpoint is the percent change from baseline in dystrophin levels (mean membrane stain density) after 40 weeks of ataluren therapy as determined by a validated IHC assay. Within each muscle location, the best, median, and the average dystrophin levels of the muscle cores will be summarized using descriptive statistics for each subject. The secondary efficacy endpoint will be analyzed using the same method as described in Section 7.1.1 (Primary Analysis). The best dystrophin levels across all muscles are considered the primary interest. As supportive analyses, the average and median dystrophin levels across all muscles, and subgroup analyses of the best, median, and mean dystrophin levels within each muscle location will be considered. In addition to dystrophin levels (the mean staining intensity), the percentage of positive fibers will also be summarized using descriptive statistics.

### 7.2.2. Sensitivity Analyses

The following analyses will be considered as sensitivity analyses for the secondary efficacy endpoint:

- PP analysis: The same secondary efficacy analysis described in Section 7.2.1 (Secondary Analysis) will be repeated based on PP population for the secondary efficacy endpoint.
- The average and median dystrophin levels (mean membrane stain density) across all muscle locations will be analyzed using the same analysis method as described in Section 7.2.1 (Secondary Analysis).
- Excluding subjects with baseline dystrophin levels [REDACTED] of the predicted levels: The same analysis described in Section 7.2.1 (Secondary Analysis) will be repeated excluding subjects with baseline dystrophin levels [REDACTED] of the predicted levels. The same analysis on the average and median dystrophin levels across all muscle locations will also be repeated excluding such subjects.
- Subgroup analysis: The subgroup analysis by muscle location will be performed on secondary efficacy endpoint as described in Section 7.1.2 (Subgroup Analyses).
- COVID-19 considerations: The Week 40 study day (defined as Week 40 biopsy date – first study drug date +1) will be added to the efficacy analysis model described in Section 7.2.1 (Secondary Analysis) as a covariate. This analysis model will be applied to the best, average, and median dystrophin levels analyses based on the ITT population.

### 7.3. Exploratory Analyses

No hypothesis testing will be performed on all exploratory endpoints. All exploratory endpoints will be summarized using descriptive statistics based on ITT population.

#### 7.3.1. Revised North Star Ambulatory Assessment

The rNSAA consists of 17 activities, each scored as 0, 1, or 2. The sum of the 16 activities (exclude head lift) will form a total score. If fewer than 13 of the 16 activities are performed, the total score will be considered missing. If from 13 to 16 activities are performed, the total score will be standardized as follows:

$$\text{Standardized total score} = \frac{\text{observed total score}}{\text{number of non-missing activities}} \times 16$$

Transformation of the total score into a linear scale ([Mayhew 2013a](#)) will also be performed.

The mean and mean change from baseline in the total score and its linear transformation will be summarized at the Baseline and Week 40 visits based on ITT population. In addition, the proportion of subjects who has lost function after 40 weeks of ataluren treatment, defined as a drop of score from 1 or 2 at baseline to a score of 0 at the Week 40 visit, will be tabulated for each activity.

#### 7.3.2. Timed Function Test

The TFTs, the time taken to run/walk 10 meters, climb 4 stairs, descend 4 stairs, and stand from supine, will be assessed at the Baseline and Week 40 visits. Subjects who cannot perform a timed function test within 30 seconds, including those who loss of ambulation or the timed function test is above 30 seconds, will be assigned a value of 30 seconds for the respective test. The mean and mean change from baseline for each timed function test will be summarized at each visit based on the ITT population.

#### 7.3.3. Creatine kinase levels

The CK levels will be assessed at the Screening and Week 40 visits. The mean and mean change from baseline of CK levels will be summarized at each visit based on the ITT population.

## 8. SAFETY EVALUATION

All safety summaries will be generated based on the safety population.

### 8.1. Adverse Events

Adverse events will be coded using the MedDRA version 23.0. A treatment-emergent adverse event (TEAE) is defined as an adverse event that occurs or worsens on or after the first dose of study drug up to 6 weeks after the last dose of study drug. Any AE with an end date prior to the first dose of the study drug will not be considered as an TEAE.

The following summaries will be provided for TEAEs:

- TEAE overview
- TEAEs by SOC and PT

If a subject has multiple events under any given SOC and PT, the subject will be counted only once under that SOC and PT. If a subject has the same AE on multiple occasions, the highest severity reported on the CRFs (“life-threatening”, “severe”, “moderate”, “mild”, “unknown”, and “not reported”) will be presented in the summaries.

In addition, subjects with treatment-emergent SAE and TEAE leading to discontinuation will also be summarized.

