### **1.3 Risk/Benefit Assessment**

Under the current standard of care, nmDMD remains a disease with devastating consequences and bleak prognosis. The progressive and irreversible effects of nmDMD underscore the importance of early intervention with treatments that have the potential to slow physical deterioration and delay the natural course of this fatal disease. While treatment with corticosteroids target the inflammatory component of the disease, additional treatments are needed to address the loss of dystrophin, the underlying cause of the disease.

The mechanism by which ataluren restores dystrophin has been established in comprehensive preclinical studies and supported in clinical evaluations. Moreover, the clinical benefit of ataluren has been demonstrated in two large randomized controlled trials Study 007 and Study 020.

This study is designed to quantitatively evaluate the increase in dystrophin protein in boys with nmDMD. The biopsy technique to be used is less invasive than the standard biopsy and is of relative low-risk to the patient. The use of two highly sensitive validated assays to evaluate dystrophin protein levels will increase the likelihood that each biopsy sample will yield interpretable results. Hence, the study design and the importance of establishing the ability of ataluren to increase dystrophin production results in a positive risk/benefit.

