### 3 STUDY DESIGN

#### 3.1 Overall Design

[figure not shown]
This is an open-label, single-arm, Phase 2 study designed to evaluate the ability of ataluren treatment to increase dystrophin protein levels in muscle cells of patients with nmDMD. The study will evaluate the levels of dystrophin before and after 40 weeks of ataluren therapy using muscle biopsies and two validated assay methods.

Approximately, 15 to 20 ataluren-naïve male subjects, aged  $\geq 2$  and  $< 8$  years of age will be administered ataluren.

Ataluren will be dosed daily 10 mg/kg in the morning, 10 mg/kg at midday, and 20 mg/kg in the evening (10, 10, 20 mg/kg).

The study will have a screening visit and 3 additional visits (Figure 1). At the screening visit, which will be performed at a patient's local site, inclusion/exclusion criteria, demographics and medical history will be assessed. In addition, blood will be drawn for genotyping to confirm that a subject carries a nonsense mutation in the dystrophin gene. For all subjects, Visit 1 and Visit 3 will occur at the same site, that of [REDACTED]. During Visit 1 and Visit 3 biopsies will be performed and used for assessing dystrophin protein levels. At Visit 1, the first dose of ataluren will be administered following the biopsy at [REDACTED] and subjects, parent/caregivers or legal guardian will be dispensed a supply of ataluren which will be administered at home. Visit 2 will be in the clinic at the subjects' local site and weight will be measured to determine if the dose of ataluren requires adjustment. Adverse events, (SAEs), and compliance will also be captured, and an additional supply of ataluren will be dispensed.

Figure 1. Study Schematic

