Dispense Drug		X	X					First dose of study drug should be administered following completion of all Baseline (Visit 1) assessments. Because of potential changes in subject body weight over time, a dose adjustment may be made based on the subject's bodyweight at Visit 2 (Week 20). Central pharmacy to dispense drug direct to subject upon completion of Visit 2.
Unused Drug Return/ Compliance			X	X		X		All used and unused study drug kits and unused sachets will be returned as directed.

**Abbreviations:** AE, adverse event; BP, blood pressure; BMI, body mass index; HR, heart rate; PK, pharmacokinetic; rNSAA, Revised North Star Ambulatory Assessment; SAE, serious adverse event; TFT, timed-function tests; ██████████, ██████████ UV, urine volume

- 1 Screening procedures must take place within 45 days of baseline visit (Visit 1).
- 2 Any screening procedure completed within and including 7 days of Visit 1 can serve as baseline and does not need to be repeated at Visit 1.
- 3 Visit 1 and Visit 3 will be performed at ██████████. Subjects may have to return to the clinic for up to 3 days for completion of assessments and biopsy.
- 4 Early termination assessments should be performed for subjects who discontinue prematurely from the study.
- 5 The follow-up visit is for subjects who terminated early/discontinued from the study. Visit to occur ~30 days after termination/discontinuation or until recovery from or stabilization of the AE, whichever comes last. The follow-up visit will also occur for subjects who decided to discontinue ataluren therapy even if they completed assessments at Visit 3.

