### 7.3.6 Describing adverse event relationship to study drug

The investigator should provide an assessment of the relationship of the AE to the study drug, ie, whether there is a reasonable possibility that the study drug caused the AE, using the considerations outlined in Table 3.

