#### **8.4.5 Safety analyses**

Evaluations of safety will be performed using the safety analysis set. The incidence of AEs and SAEs will be tabulated using frequency count. Change from baseline results will be presented for clinical laboratory values and vital signs.

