## 2. STUDY DESIGN

[figure not shown]
This is an open-label, single-arm, Phase 2 study designed to evaluate the ability of ataluren treatment to increase dystrophin protein levels in muscle cells of patients with nonsense mutation Duchenne muscular dystrophy (nmDMD). The study will evaluate the levels of dystrophin before and after 40 weeks of ataluren therapy using muscle biopsies and two validated assay methods.

Approximately, 15 to 20 ataluren-naïve male subjects, aged  $\geq 2$  and  $< 8$  years of age will be administered ataluren.

Ataluren will be dosed daily 10 mg/kg in the morning, 10 mg/kg at midday, and 20 mg/kg in the evening (10, 10, 20 mg/kg).

The study will have a screening visit and 3 additional visits (Figure 1). At the screening visit, which will be performed at a patient's local site, inclusion/exclusion criteria, demographics and medical history will be assessed. In addition, blood will be drawn for genotyping to confirm that a subject carries a nonsense mutation in the dystrophin gene. For all subjects, Visit 1 and Visit 3 will occur at the same site, that of [REDACTED]. During Visit 1 and Visit 3 biopsies will be performed and used for assessing dystrophin protein levels. At Visit 1, the first dose of ataluren will be administered following the biopsy at [REDACTED] and subjects, parent/caregivers or legal guardian will be dispensed a supply of ataluren which will be administered at home. Visit 2 will be in the clinic at the subjects' local site and weight will be measured to determine if the dose of ataluren requires adjustment. Adverse events (AE), serious adverse events (SAE), concomitant medications, and compliance will also be captured, and an additional supply of ataluren will be dispensed.

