#### 4.5. Safety Population

This analysis set will include all subjects who received at least one dose of ataluren and will be used for all safety summaries.

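### SAP 8.1 summarises only treatment-emergent events, so biopsy or sedation harms that start before the first dose can miss every planned table and later ones are not shown separately

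*SAP*

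**What the plan says.** **Which events are tabulated.** Under SAP 8.1 an AE is treatment-emergent if it "occurs or worsens on or after the first dose of study drug up to 6 weeks after the last dose of study drug". An AE that ended before the first dose is excluded outright. The summaries named are a TEAE overview, TEAEs by SOC and PT, treatment-emergent SAEs, and TEAEs leading to discontinuation. SAP 4.5 sets the population: "This analysis set will include all subjects who received at least one dose of ataluren and will be used for all safety summaries".

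**What the protocol promises.** Protocol 7.3.8 starts AE reporting on the date of consent. Protocol 8.4.5 states: "The incidence of AEs and SAEs will be tabulated using frequency count". It sets no treatment-emergent limit, but it does place the safety evaluation in the safety analysis set.

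**Order of events at Visit 1.** SAP 2 states: "At Visit 1, the first dose of ataluren will be administered following the biopsy". The schedule of assessments agrees: "First dose of study drug should be administered following completion of all Baseline (Visit 1) assessments". Protocol 3.1.1 offers propofol and fentanyl sedation for the biopsies, which are taken at Visit 1 and Visit 3.

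**Causality.** Protocol 7.3.6 states: "The investigator should provide an assessment of the relationship of the AE to the study drug". The alternative explanations listed as examples in Table 3 do not include the study biopsy or sedation.

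**Declared changes.** SAP 10 lists three changes from the protocol. They concern the significance level, keeping subjects whom the protocol would have excluded on baseline dystrophin, and matching sensitivity analyses. None concerns AE summaries.

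**The concern.** The biopsies and the sedation offered with them are risks that the study itself imposes on boys aged 2 to under 8. One of the two planned sessions comes before any drug is given. A summary that opens at the first dose is the usual way to describe a drug's safety, but it suits the harms of a pre-dose procedure poorly.

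After the first dose the difficulty changes. There is no control arm undergoing the same biopsies, so procedural and drug-related events cannot be separated by comparing groups. Only a flag, a time window or a table by relationship can do it, and SAP 8.1 names none of these.

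Two things are at stake. Readers of the planned tables could not check the risk/benefit statement in protocol 1.3 that "The biopsy technique to be used is less invasive than the standard biopsy and is of relative low-risk to the patient". The TEAE profile reported for ataluren would also contain an unidentified share of biopsy events.

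**Working it through.** The plan states no figure to reproduce. The check applies the SAP 8.1 definition to each way a biopsy or sedation event can fall in time.

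**Inputs**
- Subjects: 15 to 20 (protocol 5.1). Biopsy visits per subject: 2 (Visits 1 and 3).
- Visit 1 can spread over up to 3 days (schedule of assessments, footnote 3), so the biopsy and the first dose may or may not share a date.
- Protocol 7.3.5 lists an onset date for each AE, but no onset time. SAP 5.2 defines study day 1 as the date of the first dose. No rule covers onset on that date.
- TEAE tail: 6 weeks after the last dose (SAP 8.1). Minimum AE reporting: 30 days after the last dose (protocol 7.3.8).

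**Classification**
1. *Starts and ends before the first dose:* expressly not a TEAE, so in no planned table, even if it is an SAE.
2. *Starts on an earlier date, continues past the first dose, does not worsen:* not a TEAE, same result.
3. *Starts earlier and worsens after the first dose:* a TEAE, so tabulated.
4. *Starts before the dose but on the same date:* undetermined. A date-only comparison makes it a TEAE; the order of events makes it not one.
5. *Starts after the first dose, from the Visit 1 biopsy:* a TEAE, pooled with all others.
6. *Follows the Visit 3 biopsy:* a TEAE if recorded and within 6 weeks of the last dose, pooled with all others.
7. *Subject biopsied but never dosed:* outside the safety population, so in no table.

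For cases 3, 5 and 6, SAP 8.1 names no table by relationship to drug and none for procedure-related events. The contents of the TEAE overview are not specified.

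**Size**
- Planned biopsy sessions: 2 × 15 = 30 to 2 × 20 = 40. This is a ceiling, because a biopsy after early termination is optional and applies only after at least 6 months of therapy.
- Sessions before the first dose: 1 × 15 = 15 to 1 × 20 = 20.

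**Capture after Visit 3.** The TEAE tail is 6 × 7 = 42 days and the guaranteed reporting period is 30 days, a gap of 42 − 30 = 12 days. Protocol 3.4 ends the study at Visit 3 for completers who continue ataluren. The follow-up visit is only for those who terminate early or stop the drug. Late Visit 3 biopsy events in continuing completers may therefore not be recorded at all.

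**The case against.** The strongest reply is that nothing is missing from the database. AEs go on the eCRF from consent with onset date, seriousness, severity and relationship to drug, and SAEs are reported within 24 hours. This stands. A reader might infer that procedural harms are lost; the documents do not support that. By-subject listings are also planned (SAP 5.1), and with 15 to 20 children a full AE listing would show much of what a table would. SAP 5.1 covers only selected domains, however, and does not name the AE domain.

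A reader might also infer that biopsy events are charged to ataluren and that nothing separates them. That too goes beyond the text. A TEAE is a label of timing, not cause. Each AE is rated for relationship to drug, Table 3 allows an unrelated rating where another explanation exists, and site-specific preferred terms would stay visible in the SOC/PT table. What remains is that no planned summary uses the rating.

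The dosed-only safety population is not an SAP departure: protocol 8.3.3 and 8.4.5 set it. A denominator of all biopsied subjects would go beyond the protocol and must be declared.

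It is tempting to put a number on the children who would carry a purely procedural TEAE. The documents give no event rate. The post-dose share of events must also differ between Visit 1, where some come before the dose, and Visit 3, where all come after the first dose. No such figure is offered.

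Finally, safety is not among the stated objectives or endpoints, and the low-risk sentence is background rationale. That lowers the priority of the point. It does not explain why protocol 8.4.5 was narrowed without a record.

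**Conclusion.** The point holds as a gap in the planned summaries. SAP 8.1 limits every AE, SAE and discontinuation table to TEAEs, protocol 8.4.5 does not, and SAP 10 is silent on the difference. Biopsy or sedation events that start before the first dose and do not worsen are in no planned table, unless onset falls on the first-dose date and dates alone are compared. Later biopsy events are tabulated but not identified as such.

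The exposure is up to 30 to 40 biopsy sessions, 15 to 20 of them before the first dose. How many events this affects cannot be derived from the documents. The conclusion assumes that SAP 8.1 lists all planned AE summaries and that the unspecified TEAE overview does not fill the gap. Severity is low: the efficacy conclusions are untouched, and the point is worth acting on because it is cheap.

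**What to change.** In SAP 8.1:
1. Tabulate AEs and SAEs from consent to first dose, in line with protocol 8.4.5.
2. Add one table, by biopsy visit, of AEs and SAEs that are procedure-related or start within a fixed window after either biopsy (for example 7 days, with 14 days as a check). Use all biopsied subjects as denominator. Fix in advance how an event is judged procedure-related, since the eCRF items in protocol 7.3.5 cover only relationship to study drug.
3. Show TEAEs with and without these events, and by relationship to drug.
4. State how an AE with onset on the biopsy or first-dose date is classified.
5. Record all of this in SAP 10, including that the denominator in item 2 goes beyond the protocol's safety set.

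The cost is SAP wording and a few tables from dates already collected. Two limits should be stated with the results. A date window will catch some unrelated events. No table can recover late Visit 3 biopsy events in completers who continue ataluren, because they have no scheduled follow-up visit.

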## **8.2. Clinical Laboratory**

Clinical laboratory assessments for hematology, biochemistry, and urine evaluations are collected at Screening, Baseline and Week 40 visits. Mean and mean change from baseline for all hematology and biochemistry laboratory assessments, and continuous variables for urinalysis will be summarized using descriptive statistics at Baseline and Week 40 visits. Categorical variables for urinalysis will be tabulated using frequency count at Baseline and Week 40 visits. In addition, shift tables for each laboratory parameters from baseline to post-baseline visits will also be provided.

Creatine kinase, summarized as an efficacy endpoint, will be excluded from all laboratory summaries and listings.

## **8.3. Vital Signs**

Vital signs including systolic blood pressure, diastolic blood pressure, pulse rate, and oral temperature are collected at Baseline and Week 40 visits. Mean and mean change from baseline for each vital sign parameters will be summarized using descriptive statistics at each visit.

## **8.4. Other Safety Assessments**

Other safety assessments including physician assessments will be presented in the subject listings only.

## **9. PHARMACOKINETIC BLOOD SAMPLE**

The PK assessments using sparse sampling and population PK modeling will be presented in a separate report. The mean, median, minimum, maximum, %CV and geometric mean of plasma concentration at pre-dose and post-dose at each visit will be summarized based on the ITT population. In case any measured plasma concentrations are below LLOQ, the plasma concentrations will be set as 0 in calculations for the statistical analysis.

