### 4.3 Exclusion Criteria

1. Ongoing intravenous (IV) aminoglycoside or IV vancomycin therapy.
2. Known contra-indication to muscle biopsy (ie. such as bleeding or clotting disorders)
3. Prior or ongoing therapy with ataluren.
4. Known hypersensitivity to any of the ingredients or excipients of the study drug (eg, refined polydextrose, polyethylene glycol 3350, poloxamer 407, mannitol 25C, crospovidone XL10, hydroxyethyl cellulose, colloidal silica, magnesium stearate).

5. Exposure to another investigational drug within 2 months prior to start of study treatment, or ongoing participation in any interventional clinical trial.
6. Requirement for daytime ventilator assistance or any use of invasive mechanical ventilation via tracheostomy. Note: Evening non-invasive mechanical ventilation such as use of bilevel positive airway pressure (Bi-PAP) therapy is allowed.
7. Elevated serum creatinine or cystatin C levels at screening. Note: If the initial test result is abnormal, it is permissible to re-test serum creatinine or cystatin C.
8. Prior or ongoing medical condition (eg, concomitant illness, psychiatric condition, behavioral disorder), medical history, physical findings or laboratory abnormality that, in the investigator's opinion, could adversely affect the safety of the subject, makes it unlikely that the course of treatment or follow-up would be completed, or could impair the assessment of study results.

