Clinical Labs	X	X		X	X	X		For Visit 1, Visit 3, and unscheduled and early termination visits, subjects should fast approximately 8 hours prior to assessment. Biochemistry and other laboratory assessments will be analyzed by the central laboratory. Biochemistry, hematology, and urinalysis laboratory assessments. Creatine kinase will be assessed via the UV method or an equivalent method. At an unscheduled visit, clinical laboratory assessments will be done as necessary. At Visit 1 and Visit 3, clinical laboratory assessments should be performed prior to biopsy.
Height/Weight/BMI		X	X	X		X		Height (in cm) and weight (in kg) will be measured at Visit 1, Visit 2, and Visit 3-Early Termination. If the subject is unable to stand, sitting arm span and ulna length should be assessed as surrogate measurements for height.
Vitals (HR & BP)		X		X	X			Vital signs will include systolic and diastolic blood pressure, pulse rate, and body temperature. The pulse rate and blood pressure determinations will be performed with the subject in a sitting position after a 5-minute rest. Blood pressure will be measured in triplicate and the average will be recorded. Vitals should be taken prior to rNSAA and TFTs assessments and biopsy.
AE/SAE Monitoring	X	X	X	X	X	X	X	AEs must be assessed and documented at each clinic visit. Subjects, parents/caregiver or legal guardian will be encouraged to report AEs of concern at any time in the intervals between visits.
Concomitant medications	X	X	X	X	X	X		Concomitant medications will need to be collected starting 30 days prior to first dose of study drug.
Efficacy Assessments								
Muscle biopsy		X		X				If a subject received ≥6 months of therapy but early terminated, a biopsy may be performed if subject, parents or legal guardian agrees.
rNSAA		X		X				
TFTs		X		X				

Study Procedure	Screening  Week (visit window)	Visit 1  Baseline Week 1	Visit 2 Week 20 (± 14 days)	Visit 3 End of Study  Week 40 (± 14 days)	Unscheduled Visit	Early Termination 	Follow-up 	Notes
Pharmacokinetic Assessments								
PK blood sampling		X		X				PK samples will be drawn on Visit 1, samples will be drawn pre-first study dose and 2 hours postdose, and on Visit 3 will be drawn pre-morning dose and 2 hours postdose.
Study Drug Administration								

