### **8.4.4 Pharmacokinetic analyses**

Plasma concentration will be summarized with descriptive statistics.

A separate analysis to evaluate the PK data observed in the study will be conducted in parallel if the plasma concentrations are within in the established therapeutic range.

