### 3.3. Sample Size Determination

Approximately, 15 to 20 ataluren-naïve male subjects, aged  $\geq 2$  and  $< 8$  years of age is planned to be enrolled in this study. Limited information is available about the magnitude and intra-subject variability of the change in dystrophin levels, as measured by an immunoassay such as ECL following 40 weeks ataluren therapy in this patient population. Assuming a baseline dystrophin level of 0.2% of control levels (as per previous dystrophin replacement therapy [Center for Drug Evaluation and research Application number: 206488Orig1s000 Eteplirsen Summary Review]), Table 1 shows the number of subjects needed to achieve an 85% power to detect an increase from baseline in dystrophin of 0.04%, 0.06% and 0.08%, for intra-subject coefficients of variability ranging from 20% to 35%, using a one-sided test at alpha 5%. As an example, if the increase from baseline is 0.08% and the intra-subject coefficient is 30%, 13 evaluable subjects would be required to have a power of 85% to detect this increase.

**Table 1: Summary of number of subjects required to achieve 85% power to detect increase in dystrophin levels from baseline**

Increase of dystrophin from baseline	Intra Subject CV			
	20%	25%	30%	35%
0.04%	19	29	41	55
0.06%	10	15	21	28
0.08%	7	10	13	18

**Abbreviations:** CV, coefficients of variability

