### 7.1. Primary Efficacy Analyses

#### 7.1.1. Primary Analysis

The primary efficacy endpoint is the percent change from baseline in dystrophin levels (final concentration) following 40 weeks of ataluren therapy, as measured by ECL. The final concentration is calculated by dividing a sample's dystrophin concentration by its total protein concentration. In addition, the percentage of the predicted levels (% normal) will also be calculated as dystrophin levels normalized to dystrophin concentration of the control population ([Syneos Health Report No. 14597.051619.A](#)):

$$\% \text{ normal (in \%)} = 100 * \text{final concentration} / 33.8$$

Within each muscle location, the best, median, and the average of the dystrophin levels and the corresponding % normal values of the muscle cores will be summarized using descriptive statistics for each subject. In case any measured dystrophin concentrations are below the lower limit of quantification (LLOQ), the dystrophin concentrations will be set at 0.5\*LLOQ in the final concentration calculation for the statistical analysis.

The null hypothesis of the primary analysis is that the percent change from baseline in dystrophin levels following 40 weeks of ataluren therapy as measured by ECL is zero with the alternative hypothesis being that the change is greater than zero. To evaluate this hypothesis, a one-sided test at the 5% significance level will be employed.

The percent change from baseline at Week 40 in dystrophin levels measured by ECL will be analyzed using the mixed effect model repeated measurement (MMRM) analysis with factors of muscle locations, visits (baseline and Week 40) as fixed effects, and subjects as a random effect, based on ITT population. An unstructured covariance matrix will be used, and if the model fails to converge, then a compound symmetry matrix will be used. Since dystrophin level is known to be non-normally distributed, a log-transformation will be used in the analysis. The best dystrophin levels across all muscles are considered the primary analysis. A sample SAS code of the MMRM model is provided as follows:

```
proc mixed data = dataset;  
  
class subjid visit mlocation; /*mlocation is muscle location*/  
  
model lnaval = visit mlocation; /*lnaval is log-transformed dystrophin level*/  
  
random subjid;  
  
repeated visit / type = un;  
  
estimate "Week 40 change from baseline" visit -1 1;  
  
run;
```

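### SAP 9 sets plasma values below LLOQ to 0 yet requests a geometric mean: it will be 0 or undefined at Visit 1 pre-dose, and at Week 40 pre-dose if any trough is below LLOQ

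*SAP*

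**What the plan says.** SAP section 9 specifies the table: "The mean, median, minimum, maximum, %CV and geometric mean of plasma concentration at pre-dose and post-dose at each visit will be summarized", in the ITT population. It then gives the rule for low values: "In case any measured plasma concentrations are below LLOQ, the plasma concentrations will be set as 0 in calculations for the statistical analysis". It makes no exception for the geometric mean and does not say when a statistic should be left uncalculated.

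The sampling times are in Table 1 of the protocol (section 7.1): "samples will be drawn pre-first study dose and 2 hours postdose, and on Visit 3 will be drawn pre-morning dose and 2 hours postdose". Protocol section 4.3 excludes "Prior or ongoing therapy with ataluren".

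Nothing elsewhere repairs the rule. Protocol section 8.4.4 says only "Plasma concentration will be summarized with descriptive statistics", and SAP section 10 (changes from the planned analyses) does not mention PK. For the dystrophin assay, SAP section 7.1.1 takes a different route: "the dystrophin concentrations will be set at 0.5\*LLOQ in the final concentration calculation for the statistical analysis".

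**The concern.** The two instructions in SAP section 9 conflict. A geometric mean is the antilog of the mean log, or equivalently the nth root of the product, and neither form works once a zero is present. At one of the four sampling times the plan creates that situation by design. At the Week 40 pre-dose time one child is enough to create it.

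The programmed output is also ambiguous. Depending on how log(0) is handled, the same data can give 0, a missing value, or a geometric mean of the quantifiable values only. The last is biased upward and rests on a different n from the mean and median beside it. The SAP does not say which is intended.

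What is at stake is one statistic in a descriptive table. It bears on a stated exploratory objective, steady-state PK after 40 weeks, and the Week 40 pre-dose row is the only trough summary that the SAP itself specifies.

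**Working it through.** No figure in the plan depends on this rule, so there is nothing to reproduce. The check evaluates the rule directly.

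**Inputs from the documents**
- Values below LLOQ become 0; geometric mean and %CV requested (SAP 9).
- Visit 1 pre-dose sample precedes the first dose (protocol Table 1), and prior ataluren is excluded (protocol 4.3).
- 15 to 20 subjects planned (SAP 3.3). The number in the ITT population with a PK sample could be smaller.

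**Assumptions**
- %CV is read as the arithmetic 100 x SD / mean; SAP 9 does not define it.
- The documents give neither the plasma LLOQ nor expected troughs, so Week 40 values are expressed in multiples of LLOQ and the chance of a low trough is varied.

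**Visit 1 pre-dose.** All n values are 0.
- Product form: (0 x 0 x ... x 0)^(1/n) = 0.
- Log form: exp(mean of log 0), with log 0 undefined.
- %CV = 100 x 0/0, undefined.
- Mean, median, minimum and maximum are all 0.

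**Week 40 pre-dose, one value below LLOQ.** Let the other n - 1 troughs all equal r x LLOQ. With the zero, the geometric mean is (r^(n-1) x 0)^(1/n) = 0 for every r and n. With 0.5 x LLOQ in its place, it is (r^(n-1) x 0.5)^(1/n):

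| n | r | Geometric mean with 0 | With 0.5 x LLOQ | Low value dropped | Arithmetic mean with 0 | Median with 0 |
|---|---|---|---|---|---|---|
| 15 | 2 | 0 | 1.82 | 2 | 1.87 | 2 |
| 15 | 10 | 0 | 8.19 | 10 | 9.33 | 10 |
| 15 | 20 | 0 | 15.6 | 20 | 18.7 | 20 |
| 20 | 2 | 0 | 1.87 | 2 | 1.90 | 2 |
| 20 | 10 | 0 | 8.61 | 10 | 9.50 | 10 |
| 20 | 20 | 0 | 16.6 | 20 | 19.0 | 20 |

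%CV also remains calculable. For n = 20 and r = 10, SD = sqrt[(19 x 0.5^2 + 9.5^2)/19] = sqrt(95/19) = 2.24, so %CV = 100 x 2.24/9.5 = 23.5%.

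**Chance that it happens.** If each child independently has probability p of a Week 40 trough below LLOQ, the chance of at least one is 1 - (1 - p)^n:

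| p (assumed) | n = 15 | n = 20 |
|---|---|---|
| 1% | 14% | 18% |
| 2% | 26% | 33% |
| 5% | 54% | 64% |
| 10% | 79% | 88% |

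**The case against.** A reader might infer that one low trough destroys the Week 40 PK results. The documents do not support that. The damage is confined to the geometric mean at the pre-dose time. The mean, median, minimum, maximum and %CV there can still be computed, and the 2-hour post-dose geometric mean is affected only if a post-dose value is itself below LLOQ.

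The Visit 1 part, though certain apart from assay background or a mistimed sample, misleads nobody. The true concentration is 0, so zeros with a blank geometric mean describe it well enough.

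The Week 40 part is conditional. The sample follows the evening dose, the largest of the day, and nothing in the documents shows that troughs would be unquantifiable. The probabilities above therefore show sensitivity to p; they are not predictions.

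The steady-state objective does not rest on this table alone. SAP section 9 sends the population PK modelling to a separate report, and protocol section 8.4.4 also foresees a separate PK analysis. Nor is the different LLOQ rule for dystrophin an inconsistency in itself: that rule feeds a log-transformed model for the primary test, whereas PK is descriptive and untested.

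All of this stands and limits the importance of the point. It does not make the rule workable. One could call the gap a mere omission to be settled in table specifications, but SAP section 9 does state a rule, and that rule cannot deliver a statistic requested one sentence before it.

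**Conclusion.** The SAP 9 rule is wrong as written, and the consequence is minor. At Visit 1 pre-dose the geometric mean is 0 or undefined and %CV is 0/0, given that ataluren-naive children have no quantifiable drug before the first dose. At Week 40 pre-dose the geometric mean is 0 or undefined if even one trough is below LLOQ. That event has a chance of 14% to 79% with 15 children and 18% to 88% with 20, for assumed independent per-child rates of 1% to 10%; the documents do not allow a narrower statement. No hypothesis test, sample size or safety conclusion is affected.

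**What to change.** Amend SAP section 9 as follows:
- Keep 0 for values below LLOQ in the mean, median, minimum, maximum and %CV, and state that %CV is the arithmetic one.
- Compute the geometric mean with 0.5 x LLOQ for values below LLOQ, the substitution already used for dystrophin in SAP 7.1.1.
- Show n (%) below LLOQ at each sampling time.
- Report the geometric mean and %CV as not calculated when all values are below LLOQ, as expected at Visit 1 pre-dose. Substitution adds nothing there, since it would only return 0.5 x LLOQ.

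The cost is a sentence or two of SAP text and one table column. The downside is that the geometric mean depends a little on the substituted value. With one low value, doubling the substitute from 0.5 x LLOQ to LLOQ multiplies the geometric mean by 2^(1/n), which is 1.047 at n = 15 and 1.035 at n = 20. The dependence grows with the number of low values, and the count below LLOQ makes it visible.
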